2.3 Sample Size

The sample size was calculated using Morgan and Case's formula with the following set-up: type I error of 0.05, power of 0.90, 1-to-1 random allocation, and variance ratio of 0.44, using a conservative assumption for the compound symmetry correlation structure. A large effect size (Cohen's d) of 0.80 was determined based on the pooled effect sizes derived from our previous study and a recent RCT. Therefore, a minimum sample size of 30 participants will be required in this pilot RCT to test for 2×3 mixed design analysis of covariance (i.e., the number of two groups with three repeated measurements, adjusted for individual differences in baseline assessments). Allowing for an attrition rate of 40% that was observed in the previous study, a total of 50 parent-child dyads (25 in each group) will be recruited.

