2.5 Randomization and Blinding

Block randomization stratified by engagement in early intervention services (awaiting vs. receiving) based on the 1-to-1 allocation ratio will be used to assign participants to the intervention or control group. The randomization sequence will be computer-generated, and allocation will be completed by another research assistant not associated with the study.

Participants and independent outcome assessors will be blinded.

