2.6 Intervention and Control Treatment

2.6.1 Intervention Treatment: Parent Coaching (OPC)

The OPC intervention comprises three components defined as the enabling domains: (1) connect – building parents' trust in the coach by using verbal and nonverbal strategies such as listening, empathizing, and partnering; (2) structure – building parents' competence by adopting a problem-solving framework of setting goals, exploring options, planning action, carrying out plans, checking performance, and generalizing; and (3) share – building parents' autonomy by reciprocally exchanging information between the coach and parents with an emphasis on eliciting parents existing knowledge. In particular, collaborative performance analysis is used to explore the options for a particular goal. In this collaborative performance analysis, the coach follows four steps: (a) identify parents' perception of what currently happens, (b) identify what they would like to happen, (c) explore barriers and bridges to the desired performance, and (d) identify their needs to take actions to achieve goals. Throughout these steps, parents are guided to find strategies to facilitate their children's performance in order to support goal achievement.

In this pilot RCT, we propose that the OPC intervention will consist of four to eight weekly (or fortnightly) sessions in correspondence with the number of goals identified by parents and the progress of the goal achievement. Each session will last 30 minutes to one hour. Depending on parents' needs, coaching sessions will be delivered in person with one or both parent(s) in therapeutic/office rooms located at participating early education and training centers, special child care centers, university campuses, or via telephone or other communication applications (e.g., Zoom or WhatsApp). Parents will be allocated to the same coach throughout the intervention period, and the coach will not be the treating therapist of their child. Because OPC focuses on coaching parents, children's attendance at the coaching sessions will be at the parents' discretion.

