2.6.2 Control Treatment: Parent Consultation

Parents who are randomized to the control treatment will receive consultation regarding community resources from occupational therapists or occupational therapy students who are not involved in OPC training or meetings in the study. A toolbox of community resources has been developed by the research team by identifying public playgrounds, play groups, and sports programs sponsored by non-governmental organizations or government from the website of the Leisure and Cultural Services Department (www.lcsd.gov.hk/en/). It also included generic supportive strategies for parents of children with disabilities, as drawn from the existing literature. Occupational therapists or master of occupational therapy students who have studied rehabilitation psychology and fundamental occupational therapy subjects will use the toolbox to provide parents with available environmental resources and strategies to enhance the community participation of their child with DD, followed by an understanding of the current situation and the identification of problems encountered by parents. The direct informing approach will be used to instruct parents about the availability of environmental resources close to their living areas and what they can plan to do by using possible supportive strategies. In addition, information about child disability and/or developmental milestones may be provided if needed. However, the OPC key elements, such as parents' involvement in the action-reflection process and collaborative performance analysis will be avoided in the consultation.

The consultations will be conducted for four to eight weekly/fortnightly sessions depending on the parents' needs, and each session may last 30 minutes to one hour. The consultations will be delivered in person or in tele-format at the parents' discretion. Prior to the study, occupational therapists and occupational therapy students will be trained by the first author in the use of the toolbox. A two-hour training session will be held including the introduction of strategies and resources included in the toolbox and the procedure to provide consultation, followed by role-play practice. They will be supervised regularly in monthly meetings throughout the study period. Parents will be allocated to the same trained therapists or students for consultation during the study period.

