2.7.2.3 Initial Efficacy of OPC

2.7.2.3.1 Primary Outcome Measures

Canadian Occupational Performance Measure (COPM). The COPM will be used to measure parents' perceptions of children's participation in specific community activities. This measure is selected for use because it can identify individualized problems in participation in occupations and then help to formulate goals related to child participation through semi-structured interviews. In the interview, parents are further prompted to rate their child's performance and their satisfaction with the current status on a 10-point Likert scale (1 = *not good/satisfied at all* and 10 = *optimal performance/satisfaction*). High scores indicate greater children's participation performance and parents' satisfaction. In this pilot RCT, we propose that parents' identified goals will not be limited to the community participation but will also be extended to other life areas. An adequate internal consistency (Cronbach's $\alpha = 0.73$ – 0.88) of the COPM has been reported. The prioritized problems using the COPM in parents of children with disabilities were also found to be corresponding with specific items in the Pediatric Evaluation of Disability Inventory, demonstrating construct validity of the COPM.

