To evaluate the initial efficacy of OPC on the primary and secondary outcomes, we will use the repeated-measures analysis of covariance (ANCOVA) by controlling for baseline variability at time 0 as well as the variations in treatment dosage and delivery format (e.g., in person or tele-format). That is, the repeated-measures ANCOVAs will be used to compare the change in the scores of outcome measures across the three time points (at times 1, 2, and 3) by controlling for baseline differences and treatment variations. For participation goals identified by parents in the COPM, only community-related participation goals will be targeted for analysis. Principles of intent-to-treat analysis will be applied and, if participants withdraw after the coaching/consultation sessions, their data for subsequent time points will be imputed by carrying the last assessment forward. Post-hoc analyses using the Schffé method will be performed when the main comparison results are significant. Statistical significance will be set at $p < 0.05$. Estimates of effect sizes with 95% confidence intervals will be calculated for each outcome measure.

TABLE 1: A priori success criteria to assess the feasibility of the trial

	Definition	Success criteria
Recruitment	Percentage of eligible families agreeing to participate in the study	$\geq 20\%$ recruitment response rate achieved
Retention	Percentage of participants who complete the trial	$\geq 60\%$ retention rate achieved (i.e., completion of all assessments)
Adherence	Percentage of coaching sessions attended by parents in the intervention group	$\geq 75\%$ adherence rate achieved, based on our previous research of similar duration (42)
Blinding success	Percentage of parents who guess treatment allocation correctly after the study	50% based on the guess of treatment by chance (50/50)
Fidelity	Degree to which the OPC is implemented by coaches as intended	$\geq 80\%$ fidelity on the OPC Fidelity Measure Version 3.0 in four selected session per coach

Note: The OPC Fidelity Measure Version 3.0 consists of 18 items across five domains: relationship, goal, reflection, analysis and action, client response, and distinguishing. Each item is rated on a 3-point Likert scale (1 = *low* and 3 = *high*). The percentage score will be calculated by dividing the total score by the possible maximum score. Higher percentage scores indicate higher fidelity, and the cut-off of sufficient fidelity of OPC per session is set at 80%.

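### The efficacy ANCOVA adjusts for treatment dosage, which arises after randomization and in the OPC arm partly reflects goal progress, so the group coefficient is not the intent-to-treat effect the plan claims

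*Combined protocol and SAP*

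**What the plan says.** Section 2.8 sets one efficacy model for all primary and secondary outcomes: a repeated-measures ANCOVA over times 1, 2 and 3, "controlling for baseline variability at time 0 as well as the variations in treatment dosage and delivery format". The next sentence restates this as control for baseline differences and treatment variations. The paragraph also states: "Principles of intent-to-treat analysis will be applied".

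Dosage is not fixed in advance, and the arms follow different rules.

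- OPC (section 2.6.1): four to eight sessions, "in correspondence with the number of goals identified by parents and the progress of the goal achievement".
- Consultation (section 2.6.2): "The consultations will be conducted for four to eight weekly/fortnightly sessions depending on the" needs of the parents.

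Format is also flexible. Under OPC it follows parents' needs. For the control arm, "The consultations will be delivered in person or in tele-format at the" discretion of the parents.

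The COPM (section 2.7.2.3.1) is used first to formulate goals and then to rate them. Goals "will not be limited to the community participation but will also be extended to other life areas", while section 2.8 analyses only the community goals.

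Other covariates appear elsewhere. Section 2.5 has "Block randomization stratified by engagement in early intervention services (awaiting vs. receiving"). Section 2.7.2.3.3 says categorized early-intervention service hours will be a control variable in the efficacy analysis. Section 2.8 names neither.

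**The concern.** Randomization balances what exists before allocation. The number of sessions does not exist then: in the OPC arm it is set partly by how well the goals are going, and in the control arm by something else. Holding it constant compares parents who had the same number of sessions for different reasons, which is not a comparison of the groups as randomized.

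The exposure is most direct for the COPM, because progress on goals helps set the covariate and is close to what the outcome scores. That is an inference from sections 2.6.1 and 2.7.2.3.1, and it is looser than one-to-one because goals outside the community may drive sessions without being analysed. For the YC-PEM, PSOC, DASS-21 and KINDL the documents state no direct link between sessions and outcome.

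At stake are the p-values and the effect sizes with 95% confidence intervals that the plan will report as initial efficacy. The estimate can be pushed either way. Even with no dosage-outcome link, power is lost whenever mean sessions differ between arms.

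**Working it through.** **1. The plan's own sample size.** Inputs from section 2.3: type I error 0.05, power 0.90, 1:1 allocation, variance ratio 0.44, d = 0.80, attrition 40%.

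n per arm = 2 × (1.960 + 1.282)² × 0.44 / 0.80² = 14.45, rounded up to 15. The total is 30, and 30 / (1 − 0.40) = 50. This reproduces "a minimum sample size of 30 participants will be required in this pilot RCT" and the 50 to be recruited. Sidedness is not stated; a one-sided test would give 24.

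The ratio 0.44 is the maximum over ρ of (1 + 2ρ)/3 − ρ², which is 4/9 at ρ = 1/3. That is the variance of the mean of three measurements adjusted for one baseline. So the calculation allows for baseline adjustment only, and it appears to rest on a group main effect.

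**2. What the dosage term does.** By least squares,

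adjusted group coefficient = total effect − γ × δ,

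where γ is the pooled within-arm slope of outcome on dosage and δ is the OPC-minus-control difference in mean dosage. The shift is zero only if γ = 0 or δ = 0. The documents give neither.

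Assumed range: γ of ±0.05 to ±0.20 SD per session and δ of ±1 to ±2 sessions. A true 0.80 then becomes anything from 0.80 − 0.20 × 2 = 0.40 to 0.80 + 0.20 × 2 = 1.20.

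Large-sample check (400,000 simulated subjects, true effect 0.80; the coefficient without dosage was 0.80 in every case):

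| Assumed rule for sessions | δ | γ | Adjusted effect |
|---|---|---|---|
| Fall with progress, OPC only | −0.59 | −0.22 | 0.67 |
| Rise with progress, OPC only | +0.59 | +0.23 | 0.66 |
| Fall with progress, both arms | −0.59 | −0.53 | 0.49 |
| Related to outcome, equal means | 0.00 | −0.24 | 0.80 |

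**3. Trial-sized simulation, true effect 0.** 6,000 trials per case; all inputs are assumptions. Time 2 model: outcome = 0.5 × baseline + residual, total variance 1, 25 per arm. OPC sessions = arm mean − 1 × progress + N(0,1), rounded and clipped to 4–8. Progress correlates 0.5 with the outcome residual (1.0 in the extreme case). Repeated-measures model: between-time correlation 0.5, with a response component shared by times 2 and 3 that drives progress; the group-by-time contrast is the mean of times 2 and 3 minus time 1. Column heads give the arm difference in sessions before clipping; cells give bias in SD.

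| Quantity tested | 0.5 | 1.0 | 1.5 | Extreme (1.5, correlation 1.0) |
|---|---|---|---|---|
| Time 2 ANCOVA | +0.07 | +0.13 | +0.20 | +0.41 |
| Rejection rate | 5% | 8% | 11% | 31% |
| Repeated measures, group main effect (rejection 5–7%; extreme 10%) | +0.02 | +0.05 | +0.08 | +0.16 |
| Group-by-time, with dosage-by-time (rejection 5–6%; extreme 12%) | +0.04 | +0.07 | +0.12 | +0.24 |
| Group-by-time, dosage as main effect only | none | none | none | none |

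With no arm difference the time 2 bias is 0.00 and rejection 5%. The last row is an algebraic identity: over 200 data sets the largest discrepancy was 1.2 × 10⁻¹⁴. At a 1.0-session difference the time 2 bias becomes −0.13 if OPC sessions rise with progress, or if control has more sessions. With 15 per arm it is still +0.13. The Monte Carlo standard error of a 5% rejection rate is √(0.05 × 0.95 / 6000) = 0.3 percentage points.

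**4. True effect 0.80, time 2 ANCOVA.**

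- Same starting mean sessions, sessions falling with progress: reported as 0.64–0.71 at correlation 0.5 and 0.49–0.62 at correlation 1.0. The lower value has the link in both arms, the upper in OPC only.
- One more OPC session, sessions rising with progress, correlation 0.5: reported as 0.58, and power falls from 89% to 46%.
- No dosage-outcome link: unbiased, but power falls from 89% to 81% (1.0-session difference) or 71% (1.5).

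Without dosage in the model, the estimate was unbiased with about 5% rejection under a true effect of 0.

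**The case against.** The best defence is that section 2.8 compares change over three time points, which points to group-by-time, and that contrast is untouched if dosage is only a between-subject main effect. The largest figures above come from a single-time model. The repeated-measures figures under moderate assumptions are modest (+0.02 to +0.12 SD, rejection 5–7%), and none were produced under a true effect. This stands as a limit on size. It does not clear the plan, because section 2.8 does not say which effect is tested or whether dosage interacts with time, and the variance ratio in section 2.3 matches a group main effect.

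Second, every input on dosage is assumed. Both arms share the same range of sessions and session length, the control is described as component-equivalent, and dosage is not defined; session count is one reading. Mean dosage could turn out equal. That is possible, but nothing in the plan secures it and the arms follow different rules. The simulations also leave out attrition and last-observation imputation, so the finding of no bias without dosage applies to complete data.

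Third, delivery format may be a pre-existing preference. Bias from it is less certain than from dosage, but the text does not say it is fixed before allocation.

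Fourth, the service-hours covariate may be what section 2.8 means by baseline differences. That reading is fair; the two sections still need to say so. Omitting the stratum is minor: it causes no bias and leaves the test slightly conservative.

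Fifth, this is a pilot whose success criteria are about feasibility. Even so, initial efficacy is a stated aim, tested at 0.05 with effect sizes for each outcome, and a shifted effect size could mislead the design of a later trial.

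**Conclusion.** The concern holds. The only efficacy model described conditions on a variable realised after randomization while the plan claims intent-to-treat, and in the OPC arm that variable depends partly on goal progress. Bias reaches the group main effect, and the group-by-time effect if dosage interacts with time; it does not reach group-by-time when dosage is a between-subject main effect only. Its size and sign cannot be derived from the documents: every figure rests on assumed dosage differences and dosage-outcome links, and the shift vanishes if either is zero. The COPM is the most exposed outcome. This should be corrected before the efficacy analysis, since the term adds nothing to an intent-to-treat estimate and removing it is nearly free.

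**What to change.** In section 2.8:

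- Remove treatment dosage and delivery format from the primary and secondary efficacy models.
- Adjust for the time 0 score and the randomization stratum (awaiting versus receiving services).
- State whether the categorized baseline service hours are also a covariate, so that sections 2.7.2.3.3 and 2.8 agree.
- State whether the tested quantity is the group main effect or the group-by-time contrast.
- Report sessions and format by arm descriptively, and place any dose- or format-adjusted model in a labelled exploratory, non-randomized analysis.

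The cost is wording only. Section 2.3 already assumes baseline adjustment alone, so 30 analysable and 50 recruited are unchanged. One degree of freedom for the stratum replaces those spent on dosage and format. No change to how either treatment is delivered is implied.

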2.7 Outcome Measures

2.7.1 Assessment timing

This pilot RCT will use four assessment points similar to the design of Graham et al.'s study. The four time points are: 5–6 weeks before intervention (time 0 for baseline assessment), 1–2 weeks before intervention (time 1 for pre-intervention assessment), 1–2 weeks after intervention (time 2 for post-intervention assessment), and 8–9 weeks after the intervention (time 3 for follow-up assessment).

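### Section 2.8 has no missing-data rule for parents who leave before or during the sessions, and its only rule, last observation carried forward, does not fit the assessment schedule

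*Combined protocol and SAP*

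**What the plan says.** Section 2.8 compares times 1, 2 and 3 by repeated-measures ANCOVA, adjusted for the time 0 score, treatment dosage and delivery format. One sentence deals with missing outcomes. It opens with "Principles of intent-to-treat analysis will be applied" and continues: "if participants withdraw after the coaching/consultation sessions, their data for subsequent time points will be imputed by carrying the last assessment forward". The document has no rule for earlier withdrawal or for a missed assessment, and no sensitivity analysis for missing data.

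Section 2.7.1 puts time 1 at 1–2 weeks before the intervention, time 2 at 1–2 weeks after it and time 3 at 8–9 weeks after it. No primary or secondary outcome is scheduled between times 1 and 2. The Session Rating Scale is taken at each session, but it is exploratory and cannot stand in for an outcome.

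On treatment length, Section 2.6.1 says "the OPC intervention will consist of four to eight weekly (or fortnightly) sessions", and Section 2.6.2 says "The consultations will be conducted for four to eight weekly/fortnightly sessions". Section 2.3 sizes the trial for efficacy at "type I error of 0.05, power of 0.90", then raises the minimum of 30 to 50 dyads: "Allowing for an attrition rate of 40% that was observed in the previous study". Table 1 counts retention of 60% as success.

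**The concern.** Three groups of leavers are treated differently, and only two of them have a rule.

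- **Before or during the sessions.** No rule is stated. A standard repeated-measures ANCOVA needs complete records and would normally drop these parents, against the intent-to-treat principle in the same sentence.
- **Between the last session and time 2.** The last assessment is time 1, so a score taken before treatment is entered as the outcome at times 2 and 3.
- **After time 2.** The time 2 score is repeated at time 3, so the follow-up meant to show whether the effect lasts is assumed rather than measured.

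The condition itself is also loose. It could mean after the last session, or at any point once sessions have begun. On the wider meaning, mid-session leavers carry time 1 forward too, and those who leave before the first session still have no rule. With 40% attrition, and with tests and confidence intervals promised, this should not be left open until the data are seen.

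**Working it through.** **The plan's own figure.** Inputs from Section 2.3: d = 0.80, alpha 0.05 (taken as two-sided), power 0.90, variance ratio 0.44. Per arm: 2 × ((1.960 + 1.282)/0.80)² × 0.44 = 32.84 × 0.44 = 14.45, rounded up to 15, so 30 in total; 30/0.6 = 50. Both figures reproduce. Expected losses are 0.40 × 50 = 20.

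**Calendar.** Midpoints of the windows in Section 2.7.1: time 1 at 1.5 weeks before, time 2 at 1.5 weeks after, time 3 at 8.5 weeks after. Sessions span 3 weeks (four weekly) to 14 weeks (eight fortnightly). Total from time 1 to time 3: 1.5 + 3 + 1.5 + 7 = 13 weeks (short), or 1.5 + 14 + 1.5 + 7 = 24 weeks (long). The documents do not say when losses occur; an even spread is assumed.

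| Period | Short: share, of 20 | Long: share, of 20 |
|---|---|---|
| Before sessions | 11.5%, 2.3 | 6.25%, 1.25 |
| During sessions | 23.1%, 4.6 | 58.3%, 11.7 |
| Last session to time 2 | 11.5%, 2.3 | 6.25%, 1.25 |
| After time 2 | 53.8%, 10.8 | 29.2%, 5.8 |

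Without a rule: 2.3 + 4.6 = 6.9 (short) and 1.25 + 11.7 = 12.9 (long), the latter about a quarter of 50.

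**Effect on the estimate.** Assume a true 0.80 SD difference at times 2 and 3 in all parents, and random dropout of 40% in each arm. A carried time 1 score holds no treatment difference, so

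estimate = 0.80 × (1 − share of analysed parents carrying time 1).

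*Literal reading, early leavers dropped:*
- Short: window share 0.4 × 0.115 = 0.046; analysed share 1 − 0.4 × 0.346 = 0.862; 0.80 × (1 − 0.046/0.862) = 0.757.
- Long: 0.80 × (1 − 0.025/0.742) = 0.773.

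*Wider reading, mid-session leavers also carry time 1 and only pre-session leavers are dropped:*
- Short: 0.80 × (1 − 0.138/0.954) = 0.684.
- Long: 0.80 × (1 − 0.258/0.975) = 0.588.

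**Target effect.** If parents who leave before or during the sessions gain nothing extra, the effect in all randomized parents is 0.80 × 0.862 = 0.69 (short) or 0.80 × 0.742 = 0.59 (long).

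**Fading effect.** Suppose the effect is 0.80 at time 2 and 0.40 at time 3. Under the literal rule, completers (0.60) contribute 0.40, parents lost after time 2 contribute 0.80, and window losses contribute 0:
- Short: (0.60 × 0.40 + 0.215 × 0.80)/0.862 = 0.48.
- Long: (0.60 × 0.40 + 0.117 × 0.80)/0.742 = 0.45.

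**No effect, unequal dropout.** With a 1 SD gain in both arms and dropout of 30% against 50%, the literal false difference is the gap in carried shares:
- Short: 0.0577/0.827 − 0.0346/0.896 = 0.031.
- Long: 0.0313/0.677 − 0.0188/0.806 = 0.023.

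**The case against.** The strongest reply is that the written rule does little harm. On the plan's calendar only 1 to 2 of 50 parents fall in the window before time 2, and 0.76 to 0.77 is close to 0.80. That stands. A reader might infer that carrying forward badly dilutes the effect. This needs losses to cluster in the window: half of them there and half after time 2 gives 0.80 × (1 − 0.20) = 0.64, and all of them there gives 0.80 × (1 − 0.40) = 0.48. Nothing in the documents supports such splits. With random dropout, no window losses and stable scores after time 2, the literal rule leaves the contrast at times 2 and 3 unbiased.

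Second, a reader might infer that the plan intends to drop early leavers. It does not say so. Dropping is what a complete-case analysis would do. The supported defect is an incomplete and ambiguous rule.

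Third, the gap between 0.77 and 0.59 is not all bias. If early leavers gain nothing extra, the wider reading comes close to the all-randomized effect, and a mixed model giving about 0.80 overstates it. This also stands.

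Fourth, the plan adjusts for dosage, which bears directly on mid-session leavers. Consider the wider reading and long schedule, with 1 SD gains, no effect and dropout of 30% against 50%. Adding sessions attended as a covariate cut the simulated false difference from 0.138 to 0.046 and rejection from 9% to 5%. With a true 0.80 SD effect and 40% dropout per arm, power rose from 55% to 65%, while the estimate stayed near 0.60. Figures for that reading adjusted for time 0 only therefore overstate the harm to power and error rates, and none are relied on here.

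Last, this is a pilot. But Section 2.3 sizes it for efficacy, and settling the rule costs little.

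**Conclusion.** The gap in the text is certain: one rule, open to two readings, and none for parents who leave before or during the sessions. The sizes are conditional. With 40% random dropout per arm spread evenly over the plan's calendar, about 7 to 13 of 20 losses have no rule. The literal rule costs 0.03 to 0.04 SD of a true 0.80. The wider reading gives 0.68 to 0.59, which counts as bias only if leavers would have gained as much as those who stayed. A fading effect at time 3 would be put at 0.45 to 0.48 instead of 0.40. The main problem is therefore that neither the handling of early leavers nor the effect being estimated is fixed in advance; a large bias from the rule as written is not shown. Both should be settled before outcome data are seen.

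**What to change.** In Section 2.8:

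1. State the target as the effect in all randomized parents, with the group difference at times 2 and 3 as the contrast.
2. Replace carrying forward, as the main analysis, with a likelihood-based linear mixed model on times 1, 2 and 3. Include the time 0 score, group, time and group-by-time, an unstructured covariance, and small-sample (for example Kenward–Roger) degrees of freedom.
3. Include every randomized parent with any of times 1 to 3, whenever they withdrew. Report those with time 0 only, and dropout by arm and period.
4. Keep carrying forward only as a sensitivity analysis, defining which withdrawals it covers.
5. Add one sensitivity analysis in which OPC leavers gain less, for example by 0 to 0.80 SD at the unobserved times.

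The cost is SAP wording and slightly more analysis; no extra data are needed. The model relies on data missing at random, which item 5 probes. It also loses some power at time 3 if scores are truly stable after time 2. Simulations with 25 per arm, adjusted for time 0 only, gave 58–70% against 61–74% for literal carrying forward under calendar timing, and 59–72% against 82–88% if all losses follow time 2. These are not powers of the plan's full model and should not be set against its 90%.

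### The gated Scheffé step in 2.8 costs power for the two post-treatment group differences, and the size of the loss is open because its family and gating term are undefined

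*Combined protocol and SAP*

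**What the plan says.** Section 2.8 plans repeated-measures ANCOVAs over times 1, 2 and 3 for the primary and secondary outcomes. They adjust for time 0 and for treatment dosage and delivery format. For follow-up testing, the Scheffé "method will be performed when the main comparison results are significant", at the 0.05 level. Effect sizes with 95% confidence intervals are promised for each outcome measure, without saying at which time or for which contrast.

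Section 2.7.1 places time 1 one to two weeks before the intervention, time 2 one to two weeks after it, and time 3 eight to nine weeks after it. Section 2.3 sizes the trial for a 2×3 design, described as "the number of two groups with three repeated measurements, adjusted for individual differences in baseline assessments".

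The plan does not list the contrasts of interest or define the Scheffé family. It does not say whether the main comparison is group, time or group-by-time.

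**The concern.** The Introduction states the efficacy aim as a comparison with parent consultation. Only two of the three analysed assessments come after treatment, so two between-group contrasts can be written down now: the adjusted difference at time 2 and at time 3. Scheffé controls error over every linear contrast in its family, and for two planned contrasts that protection is paid for in power.

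The step is also conditional. If the gating test is group-by-time, a real effect present at both post-treatment times can go untested because the gate fails. And since the family and gate are undefined, the same sentence allows very different penalties, and the choice could be made after the data are seen.

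**Working it through.** **Inputs from section 2.3.** "type I error of 0.05, power of 0.90, 1-to-1 random allocation, and variance ratio of 0.44"; Cohen's d "of 0.80 was determined based on the pooled effect sizes"; "a minimum sample size of 30 participants will be required in this pilot RCT"; 40% attrition, giving 50 recruited (25 per arm). Sidedness is not stated. Two-sided is assumed because it reproduces 30, whereas one-sided gives 24.

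**Reproducing the plan's figure.** n per arm = 2 × (1.960 + 1.282)² × 0.44 / 0.80² = 14.45, rounded up to 15, so 30 in total; 30 / (1 − 0.40) = 50. The 0.44 matches the largest value over ρ of (1 + 2ρ)/3 − ρ². At ρ = 1/3 this is 0.5556 − 0.1111 = 0.444, the variance factor for the mean of three measurements adjusted for one baseline. The stated power therefore concerns the averaged comparison, and it is met (91% at 15 per arm).

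**Power for a group difference at one time.** The within-person correlation ρ is not given. I assume 0.33 (the value implied by 0.44) to 0.70. With adjustment for time 0 the variance factor is 1 − ρ², so the noncentrality is d × √(n/2) / √(1 − ρ²):
- 15 per arm, ρ = 1/3: 0.80 × √7.5 / √0.889 = 2.32
- 15 per arm, ρ = 0.70: 0.80 × √7.5 / √0.51 = 3.07
- 25 per arm: 3.00 and 3.96

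Error df are 2n − 3, that is 27 or 47. The Scheffé critical value is √(q × F(0.95; q, df)), where q is the dimension of the family. I take q = 1 as the group main effect, q = 2 as the two post-treatment differences (the group-by-time term also has 2 df), q = 3 as the group differences at all three times, and q = 5 as all six cell means. The dosage and delivery covariates are ignored.

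| Method | Critical t, 27 df | Power, 15 per arm (ρ 0.33 to 0.70) | Power, 25 per arm (ρ 0.33 to 0.70) |
|---|---|---|---|
| Unadjusted (same as Scheffé q = 1) | 2.05 | 61% to 84% | 84% to 97% |
| Bonferroni over two | 2.37 | 49% to 75% | 75% to 95% |
| Scheffé q = 2 | 2.59 | 41% to 68% | 68% to 92% |
| Scheffé q = 3 | 2.98 | 28% to 54% | 54% to 85% |
| Scheffé q = 5 | 3.59 | 13% to 33% | 33% to 68% |

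Against Bonferroni over two, the loss at 15 per arm is 7 to 8 points (q = 2), 21 to 22 (q = 3) or 36 to 42 (q = 5). At 25 per arm it is 3 to 7, 10 to 21 or 26 to 42.

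**The gate.** Within a family, the largest squared contrast t equals q × F. No Scheffé contrast can therefore be significant unless the F test for that same family is, and such a gate costs nothing extra. A different gate can cost more. I simulated d = 0.80 at times 2 and 3 and no effect at time 1, with the group-by-time F as gate:
- 15 per arm: the gate passes in about 46% to 81% of trials. At least one of the two contrasts is significant in about 69% to 88% with ungated Bonferroni, against 35% to 71% with the gate and Scheffé q = 2.
- 25 per arm: the gate passes in about 70% to 97%. The comparison is about 90% to 99% against 65% to 95%.

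Adjusting the gating F for time 0 changes its pass rate by only one or two points.

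**The case against.** The strongest reply has five parts.

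1. The documents nowhere say that only times 2 and 3 matter. Section 2.8 compares change across three times, which could include within-group change or maintenance, and in a group-by-time test time 1 is the reference for change. This stands: the two contrasts are an inference from the aim and the assessment schedule. The inference is a direct one, because those are the only times at which treatment can separate the arms.

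2. A reader might infer that Scheffé undermines the 90% power in section 2.3. The documents do not support that. The 90% belongs to the averaged 2×3 comparison, and no power is promised for post-hoc contrasts. At 15 per arm a single time has only 61% to 84% power with no adjustment at all, so part of the distance from 90% is not due to Scheffé.

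3. The gate may be harmless. This stands if it covers the same family as the contrasts.

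4. The analysed number may exceed 30, because 2.8 carries the last assessment forward for participants who withdraw after the sessions. The 25-per-arm column is the upper bound, and there the 2-df loss can be as small as 3 points.

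5. Scheffé is valid and errs on the safe side, this is a pilot, and intervals are already promised with no significance condition. All true, and this limits the severity. But the intervals are not tied to a time or contrast, so the promise does not secure the two estimates.

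**Conclusion.** The point holds in limited form. For two group differences that can be named in advance, the gated Scheffé step has less power than planned contrasts whenever its family has 2 df or more. The loss runs from zero (1-df group effect) to about 42 points (all six cells), and the documents do not say which applies. These figures rest on d = 0.80, two-sided 0.05, 15 to 25 per arm, adjustment for time 0 under compound symmetry, and an assumed ρ of 0.33 to 0.70.

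It would be too strong to say that the trial is underpowered for its main comparison, that the gate always adds a penalty, or that the six-cell family is what the plan intends. N = 30 and the target of 50 reproduce, a matching gate is free, and the family is not stated. Neither bias nor an inflated false-positive rate follows. Severity: minor to moderate.

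**What to change.** In 2.8, replace the gated Scheffé sentence with something like: for each outcome, the baseline-adjusted difference between OPC and parent consultation will be estimated at time 2 and at time 3, each with a 95% confidence interval, whatever the result of the omnibus test; statements of significance will use Holm's procedure over these two contrasts.

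This takes one sentence and no extra participants. It removes a choice that could otherwise be made after the data are seen, and it yields the time-specific estimates a later trial would need. Holm is at least as powerful as the Bonferroni figures above. The small cost is the loss of protection for unplanned contrasts such as within-group change or maintenance, which can be reported descriptively. Holm over two controls error within each outcome only; multiplicity across outcomes is left as it is now.
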